### 5.4.1 Entinostat/Placebo Dose Modifications

#### 5.4.1.1 Special Considerations

For any grade 4 toxicity that recurs despite prophylaxis or dose reduction, protocol treatment should be permanently discontinued.

Any consideration of changes to these dose modification guidelines must be discussed with the Study Chair for approval in advance.

**NOTE:** If a patient experiences a grade 3 or 4 event that requires a dose modification after dose has previously been reduced, entinostat/placebo should be omitted for 2 weeks and continued at the reduced dose of 3mg.

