#### 5.1.1 Arm X (Arms A and B)

Exemestane 25mg po (single dose), days 1-28

Entinostat/placebo 5mg po (single dose), days 1, 8, 15, and 22

Rev. 10/15

Goserelin (Pre/perimenopausal female and all male participants only):  
3.6 mg SubQ injection day 1

Repeat cycles every 28 days until development of disease progression per Section [6](#) or unacceptable toxicity.

**NOTE:** The patient will be randomized to Arm A (Entinostat) or Arm B (placebo), but as this is a double-blind trial, all patients will be identified as on Arm X.

Rev. 10/16

The schedule should be followed as closely as is realistically possible; however, the schedule may be modified due to problems such as scheduling delays or conflicts (e.g., clinic closure, poor weather conditions, vacations, etc.) with the guidance of the protocol chair/designee, as appropriate, and will not be reportable as a deviation unless the endpoints of the study are affected.

Rev. Add5

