## 5.4 Dose Modifications

Although entinostat and exemestane have distinct toxicity profiles, they do share some adverse events such as fatigue, nausea, and diarrhea. There is the theoretical possibility that one agent may potentiate the other and hence drug causality will not always be clear. In the event of uncertainty, dose reductions and/or delays will follow the most conservative approach.

Treatment will be modified based on treatment-related toxicity as described below for all patients receiving entinostat/placebo. Dose omits due to toxicity will not be made-up; patients may resume treatment once toxicity resolves as per the regular schedule. Dose reductions due to toxicity are permanent. Dose escalation is not allowed.

If more than two doses of entinostat/placebo are omitted in a single cycle due to entinostat/placebo-related toxicity, the patient will be permanently discontinued from protocol therapy, followed until event resolution, and managed at the investigator's discretion. Exemestane may continue in this case.

Regular dosing and compliance with medication is strongly encouraged. If  $\geq 2$  doses of entinostat/placebo per cycle are omitted for reasons other than toxicity in  $> 2$  cycles, the patient will discontinue protocol therapy. However, if the treating investigator believes the subject is benefitting from treatment and feels it is in the best interest of the participant to continue on study, exceptions may be considered after discussion with the Study Chair.

Prior to administration of first dose of entinostat/placebo in each cycle, patient's organ function must have recovered to the following values:

Minimum Values for Dose Administration	
Absolute Neutrophil Count	$\geq 1 \times 10^9/L$
Platelets	$\geq 50 \times 10^9/L$
Creatinine	$\leq 2 \times$ institutional upper limit of normal (ULN)

**NOTE:** The dose modifications noted below refer to administration of entinostat/placebo. Exemestane dose reductions are not allowed. If exemestane administration is held for any reason, patient can remain on study for up to 7 days. If exemestane administration is held for  $> 7$  days, patient will be considered off protocol treatment.

**All toxicity grades below are described using the NCI Common Terminology Criteria for Adverse Events (CTCAE) version 4.0.**

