**Table 5.4.1: Dose Reductions for Entinostat/Placebo-Related Toxicity**

Hematologic Toxicity			
CTCAE System Organ Class (SOC)	Adverse Event	Grade	Entinostat/Placebo Dose Change
Investigations	Neutrophil count decreased	Grade 1 or 2	No change
		Grade 3 or 4	Omit for 2 weeks and reduce to 3mg
	Platelet count decreased	Grade 1 or 2	No change
		Grade 3 or 4	Omit for 2 weeks and reduce to 3mg
	White blood cell decreased	Grade 1 or 2	No change
		Grade 3 or 4	Omit for 2 weeks and reduce to 3mg
Non-Hematologic Toxicity			
CTCAE System Organ Class (SOC)	Adverse Event	Grade	Entinostat/Placebo Dose Change
Gastrointestinal disorders	Diarrhea (Reduce dose only after optimal use of loperamide)	Grade 1 or 2	No change
		Grade 3 or 4	Omit for 2 weeks and reduce to 3mg
	Nausea / Vomiting (Reduce dose only after optimal use of anti-emetics)	Grade 1 or 2	No change
		Grade 3 or 4	Omit for 2 weeks and reduce to 3mg
Metabolism and nutrition disorders	-Hyperglycemia -Hypoglycemia -Hypophosphatemia -Hypernatremia -Hyponatremia -Hypercalcemia -Hypocalcemia	Grade 1 or 2	No change
		Grade 3 or 4	Omit for 2 weeks and reduce to 3mg
Other non-hematologic adverse events not mentioned above		Grade 1 or 2	No change
		Grade 3 or 4	Omit treatment until toxicity resolves to Grade 1 then dose reduce to 3mg

Unless otherwise specified, grade 3 or 4 toxicity should improve to grade 2 or better prior to resuming treatment

---

If more than two doses of entinostat/placebo are omitted in a single cycle due to entinostat/placebo-related toxicity, the patient will be permanently discontinued from protocol therapy

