#### 5.7 Duration of Therapy

Patients will receive protocol therapy unless:

- Progressive disease by RECIST criteria. See Section [6.1](#).
- Severe toxicity at discretion of treating physician or unresolved Grade 3 or 4 toxicity.
- Extraordinary Medical Circumstances: If at any time the constraints of this protocol are detrimental to the patient's health, protocol treatment should be discontinued. In this event, submit forms according to the instructions in the E2112 Forms Packet.
- Patient withdraws consent.
- Exemestane or entinostat/placebo is held for longer than permitted per Section [5.4](#).
- Patient receives non-protocol therapy, including chemotherapeutic or investigational anti-neoplastic drugs or radiation therapy to only lesion available to monitor response.

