#### 9.7 Adherence to Protocol Therapy

Another secondary objective of the study is to measure adherence to protocol therapy. Patient's adherence to protocol therapy will be quantified using pill count (entinostat/placebo) and diary methods (exemestane). The number of pills a patient has taken will be recorded for every cycle (4 weeks). Patients will be instructed to bring their medication bottles (entinostat/placebo) and diaries (exemestane) with them for clinic visits. Clinic or pharmacy staff will count the number of remaining pills (entinostat/placebo) or pill diary doses taken (exemestane), and will calculate the number of pills taken using a treatment form. As administration of entinostat/placebo is weekly, it will be 0-4 doses per cycle.

Dose reduction (from 5mg to 3mg) is allowed for entinostat/placebo due to toxicity in the trial. If more than two consecutive doses of entinostat/placebo, or > two doses of entinostat/placebo per cycle are omitted due to toxicity, the patient will be permanently discontinued from protocol therapy. For exemestane, it will be administered once daily in each cycle, it will be 0-28 pills per cycle. Exemestane dose reductions are not allowed. If exemestane administration is held for > 7 days due to any reason, patient will be considered permanently off protocol treatment.

The adherence score will be calculated as the proportion of the total number of pills a patient actually took over the whole treatment period divided by the total

number of pills a patient should have taken. The strength of doses will be taken into account and the reduced dose of 3mg will be counted as 0.6 full dose (5mg) in adherence score calculation. The timing of doses will not be considered in the study. Data about adherence to protocol therapy will be collected for exemestane and entinostat /placebo separately for each arm. The adherence score will be calculated for each patient for each agent (exemestane and entinostat /placebo) separately. For the evaluation of each agent, patients will be categorized into 3 groups based on the adherence score. An adherence score of > 85% will be considered as high adherence, and an adherence score of < 65% will be considered as low adherence, and patients with an adherence score of 65%-85% will be considered as medium adherence.

Rev. Add7

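### Section 5.4.1.1 gives two incompatible instructions for a grade 4 toxicity that recurs in a patient already reduced to 3 mg: stop permanently, or hold for 2 weeks and resume 3 mg

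*Combined protocol and SAP*

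**What the plan says.** Section 5.4.1.1 (Special Considerations) contains two rules a few lines apart.

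- Stop rule: "For any grade 4 toxicity that recurs despite prophylaxis or dose reduction, protocol treatment should be permanently discontinued".
- NOTE, trigger: "If a patient experiences a grade 3 or 4 event that requires a dose modification after dose has previously been reduced".
- NOTE, action: "entinostat/placebo should be omitted for 2 weeks and continued at the reduced dose of 3mg".

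Section 5.4 makes toxicity-related reductions permanent and rules out re-escalation. Table 5.4.1 offers one reduced dose, 3 mg, and puts grades 3 and 4 in the same row with the same action for every toxicity listed. Its first footnote adds that, unless otherwise specified, "grade 3 or 4 toxicity should improve to grade 2 or better prior to resuming treatment".

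The automatic limits on omitted doses are in Section 5.4 and the second footnote of Table 5.4.1, which end protocol therapy if "more than two doses of entinostat/placebo are omitted in a single cycle due to entinostat/placebo-related toxicity". Section 9.7 repeats the per-cycle limit and adds a consecutive-dose version: "If more than two consecutive doses of entinostat/placebo". Section 5.7 lists as a reason to stop: "Severe toxicity at discretion of treating physician or unresolved Grade 3 or 4 toxicity".

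**The concern.** The stop rule expressly covers recurrence despite a dose reduction. The NOTE expressly covers grade 4 events after a dose reduction and makes no exception for recurrence. One patient can therefore satisfy both, with opposite instructions.

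A site that follows the NOTE to the letter would give more study drug, at the lowest protocol dose, to a patient who has already had recurrent grade 4 toxicity. A site that follows the stop rule would end treatment for the same event. Beyond patient safety, the summary of adverse events leading to discontinuation (Section 9.4) would then depend partly on which sentence a site relied on.

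**Working it through.** The plan gives no figure to reproduce. The check has three parts: whether the triggers overlap, whether the omitted-dose limits settle the matter, and whether any other text does.

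**1. Overlap of the two triggers, for a patient already at 3 mg**

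| Event | Stop rule applies? | NOTE applies? |
|---|---|---|
| Grade 3 event | No | Yes |
| First grade 4 event of a different type | No | Yes |
| Recurrence of a grade 4 toxicity | Yes: stop permanently | Yes: hold 2 weeks, resume 3 mg |

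Only the last row conflicts. It is an ordinary path through the table: a first grade 4 event takes the patient to 3 mg, and the same event recurring there meets both rules. Because there is one reduced dose and reductions are permanent, anyone whose toxicity recurs despite a reduction has by definition been reduced before. The NOTE therefore overlaps the whole of the dose-reduction part of the stop rule.

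**2. Omitted-dose limits**

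The schedule in Section 5.1.1 is "Entinostat/placebo 5mg po (single dose), days 1, 8, 15, and 22", that is, 4 weekly doses per 28-day cycle. A 2-week hold of a weekly drug omits 2 doses:

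| Hold starts | Doses omitted | Most in one cycle | Consecutive |
|---|---|---|---|
| Day 1 | Days 1, 8 | 2 | 2 |
| Day 8 | Days 8, 15 | 2 | 2 |
| Day 15 | Days 15, 22 | 2 | 2 |
| Day 22 | Day 22, next cycle day 1 | 1 | 2 |

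The limits require more than 2, per cycle (Section 5.4, Table 5.4.1, Section 9.7) or consecutively (Section 9.7). The maximum here is 2, so the limits are reached for 0 of 4 start days. This assumes no other toxicity omission in the same cycle and recovery in time to resume: grade 2 or better unless otherwise specified, plus the Section 5.4 minimum blood count and creatinine values if the next dose opens a cycle.

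**3. Other text that might settle it**

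- The sentence in Section 5.4 on taking the most conservative approach follows a remark about unclear drug causality. It refers to reductions and delays, not to discontinuation.
- Section 5.7 covers physician discretion and toxicity that has not resolved. It sets no rule for a recurrent grade 4 event that does resolve.
- Study Chair approval under Section 5.4.1.1 is needed to change the guidelines. A site following the NOTE is not changing them, so nothing prompts it to call.

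**The case against.** The best counter-argument is that the text already has a coherent, safe reading. The NOTE is limited to events that require a dose modification, and a recurrent grade 4 toxicity could be said to require discontinuation instead. Moreover, if the NOTE prevailed, the stop rule's reference to dose reduction would have no effect. If the stop rule prevails, both sentences keep a role, since the NOTE still tells sites what to do when the table says to reduce and the patient is already at 3 mg. The specific rule would then override the general one. The sequence is also narrow, and no frequency is given.

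Much of this stands. The reconciling reading is sensible and probably what was intended, and the scope is small. For toxicities in the table's residual non-hematologic row, recovery to grade 1 is required with no fixed 2-week hold, so the omitted-dose limits may stop more of those patients. Section 5.7 discretion will stop others.

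The argument does not remove the conflict. Table 5.4.1 assigns a dose change to grade 3 or 4 in every row, so the NOTE's condition is literally met, and the stop rule itself sits under the heading of dose modifications. Neither rule is a pure subset of the other: the stop rule also covers recurrence despite prophylaxis, and the NOTE also covers grade 3. A NOTE placed after a rule can equally be read as qualifying it. A site has to infer the precedence, because the protocol does not state it.

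**Conclusion.** The concern holds. Two stated safety rules contradict each other as written, in one sequence: the patient is already at 3 mg, a grade 4 toxicity recurs, it recovers in time for a 2-week hold to end, there is no other toxicity omission in that cycle, and the physician does not stop treatment on discretion. In that sequence no automatic limit intervenes.

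No patient count can be given, and whether sites would actually diverge is not shown by the documents. The primary PFS and OS comparisons are by assigned treatment (Sections 9.2.1 and 9.2.2) and are unaffected. The point is minor in scope, but it should be corrected because it concerns re-exposure after recurrent grade 4 toxicity.

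**What to change.** Add an exception to the NOTE in Section 5.4.1.1, along these lines: *this does not apply when a grade 4 toxicity has come back after prophylaxis or a reduction; the permanent discontinuation rule above then governs.* The NOTE stays as it is for grade 3 events and for a first grade 4 event of a different type.

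While editing, it would help to say whether recurrence includes a first grade 4 event of the same type as the grade 3 event that led to the reduction, since the current wording leaves that open.

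The exception is one clause. It changes nothing in the sample size, visit schedule or analyses.

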**Table 5.4.1: Dose Reductions for Entinostat/Placebo-Related Toxicity**

Hematologic Toxicity			
CTCAE System Organ Class (SOC)	Adverse Event	Grade	Entinostat/Placebo Dose Change
Investigations	Neutrophil count decreased	Grade 1 or 2	No change
		Grade 3 or 4	Omit for 2 weeks and reduce to 3mg
	Platelet count decreased	Grade 1 or 2	No change
		Grade 3 or 4	Omit for 2 weeks and reduce to 3mg
	White blood cell decreased	Grade 1 or 2	No change
		Grade 3 or 4	Omit for 2 weeks and reduce to 3mg
Non-Hematologic Toxicity			
CTCAE System Organ Class (SOC)	Adverse Event	Grade	Entinostat/Placebo Dose Change
Gastrointestinal disorders	Diarrhea (Reduce dose only after optimal use of loperamide)	Grade 1 or 2	No change
		Grade 3 or 4	Omit for 2 weeks and reduce to 3mg
	Nausea / Vomiting (Reduce dose only after optimal use of anti-emetics)	Grade 1 or 2	No change
		Grade 3 or 4	Omit for 2 weeks and reduce to 3mg
Metabolism and nutrition disorders	-Hyperglycemia -Hypoglycemia -Hypophosphatemia -Hypernatremia -Hyponatremia -Hypercalcemia -Hypocalcemia	Grade 1 or 2	No change
		Grade 3 or 4	Omit for 2 weeks and reduce to 3mg
Other non-hematologic adverse events not mentioned above		Grade 1 or 2	No change
		Grade 3 or 4	Omit treatment until toxicity resolves to Grade 1 then dose reduce to 3mg

Unless otherwise specified, grade 3 or 4 toxicity should improve to grade 2 or better prior to resuming treatment

---

If more than two doses of entinostat/placebo are omitted in a single cycle due to entinostat/placebo-related toxicity, the patient will be permanently discontinued from protocol therapy

## 5.5 Supportive Care

5.5.1 All supportive measures consistent with optimal patient care will be given throughout the study.

### 5.5.2 Bone-modifying agents

Patients may be treated with bone modifying agents such as bisphosphonates or RANK-ligand agents (e.g. denosumab) per ASCO guidelines. Whenever possible, patients requiring bone modifying agents should start treatment 7 days prior to study therapy and should continue the same agent throughout study unless clinically compelled to change.

### 5.5.3 Hypersensitivity Reactions

Hypersensitivity reactions to exemestane or entinostat/placebo should be managed as per standard of care at the treating institution. Severe reactions, such as hypotension requiring treatment, dyspnea requiring bronchodilators, angioedema or generalized urticaria require immediate discontinuation of study drug administration and aggressive symptomatic therapy. Subjects who experience a severe hypersensitivity reaction to treatment should not be re-challenged.

### 5.5.4 GI Medications

Drugs used to reduce the acidity (increase pH) of the stomach, i.e. H2 antagonists, proton-pump inhibitors, antacids, etc., could potentially interfere with entinostat absorption. **Delay administration of H2-antagonists, antacids, or proton pump inhibitors, or other drugs that lower acidity for at least 2 hours after dosing entinostat/placebo.**

### 5.5.5 Nausea and Vomiting

Nausea and vomiting after entinostat/placebo administration are expected. Prophylactic 5-HT3 serotonin receptor antagonist will be administered prior to ingestion of entinostat/placebo as well as on an as needed basis. Other anti-emetic medications (prochlorperazine, lorazepam, etc.) may also be taken for delayed nausea as needed.

### 5.5.6 Diarrhea

If diarrhea occurs during dosing, an antidiarrheal agent(s) may be used. Loperamide may be taken in the following manner: 4 mg at the first onset of diarrhea, then 2 mg every two hours (4 mg every 4 hours while asleep) around the clock until diarrhea-free for at least 12 hours. Additional or institutional standard antidiarrheal measures may be used at the discretion of the treating physician.

### 5.5.7 Neutropenia without fever

The clinical situation should be closely followed for fever, focal signs of infection, and neutrophil nadir. Growth factor support should be administered in accordance with ASCO guidelines.

- 5.5.8 Neutropenia with fever  
Hospitalization and urgent broad-spectrum antibiotics are required for this potentially life-threatening complication. The occurrence of a temperature higher than 38.3°C (100.9°F) demands prompt evaluation of blood counts and examination for source of infection. Growth factor support should be administered in accordance with ASCO guidelines.
- 5.5.9 Anemia  
Red blood cell support should be given for any patient with symptomatic anemia and is recommended for patients with asymptomatic anemia when hemoglobin is below 8 g/dL.
- 5.5.10 Platelet Count Decrease  
Platelet transfusion should be given for a platelet count below 10,000/mm^3 in the absence of bleeding. If bleeding develops or invasive procedures are planned, platelet transfusion should be administered in accordance with standard practice.

## 5.6 Patient-Reported Outcomes Administration

A detailed description of the PRO measures to be administered has been included in Section [6.2](#).

- 5.6.1 PRO Instruments to be administered:
- 1) The Functional Assessment of Cancer Therapy–General (FACT-G); 27 items
  - 2) The PROMIS Fatigue 7-item Short Form
  - 3) The Functional Assessment of Anorexia/Cachexia Treatment (FAACT; 12 items)
  - 4) Functional Assessment of Chronic Illness Therapy-Diarrhea (FACIT-D; 11 items)
  - 5) FACT-Breast Symptom Index (FBSI; 8 items) – taken from 8-item FBSI outlined by Yost et al that has event-based anchor points
  - 6) Medication Adherence Scale

Rev. Add7

- 5.6.2 PRO-CTCAE items to be administered:  
Select PRO-CTCAE items (16 items) will be administered to measure patient reporting of AEs.

Rev.4/15

- 5.6.3 Patient-Reported Outcomes Assessment Schedule
- 5.6.3.1 Brief symptom index to evaluate TTD: we plan to use 6 items from the FBSI -- FACT Breast Symptom Index to detect symptom deterioration. These 6 items have been selected to focus on proximal change in symptoms. However, we will collect all 8 of the items from the FBSI 8 outlined by Yost et al. These items will be administered at the following times:
- 1) Baseline (before Cycle 1 Day 1)

- 
- 2) End of Every Cycle for Cycles 1-6
  - 3) End of Cycles 8, 10, and 12
  - 4) Then administered on the same schedule as tumor assessments until disease progression (Note, for FBSI there are not assessments planned at or post progression).
- 5.6.3.2 PRO measures of treatment toxicities (PROMIS Fatigue, FAACT, FACIT-D) will be administered at the following time points:
- 1) Baseline (before Cycle 1 Day 1)
  - 2) End of Cycle 3
  - 3) End of Cycle 6
  - 4) End of Cycle 12
  - 5) At end of protocol treatment, including treatment discontinuation for any reason (i.e. toxicity, progression, completion of protocol therapy)
  - 6) 4-weeks after end of protocol treatment, including treatment discontinuation for any reason (i.e. toxicity, progression, completion of protocol therapy).
- Rev. Add7 5.6.3.3 The ECOG-ACRIN Medication Adherence Scale Modified from the Morisky Index will be administered:
- 1) End of Cycle 3
  - 2) End of Cycle 6
  - 3) End of Cycle 12
  - 4) At end of protocol treatment, including treatment discontinuation for any reason (i.e. toxicity, progression, completion of protocol therapy)
- 5.6.3.4 Patient-reported HRQL will be assessed using the FACT-G and will be administered:
- 1) Baseline (before Cycle 1 Day 1)
  - 2) End of Cycle 3
  - 3) End of Cycle 6
  - 4) End of Cycle 12
  - 5) At end of protocol treatment, including treatment discontinuation for any reason (i.e. toxicity, progression, completion of protocol therapy)
- Rev. Add5 5.6.3.5 PRO-CTCAE: PRO-CTCAE items will be administered
- 1) Baseline and prior to every cycle, following the same schedule as trial symptom/toxicity assessments.
  - 2) End of each Cycle during treatment
-

- 3) At end of protocol treatment, including treatment discontinuation for any reason (i.e. toxicity, progression, completion of protocol therapy)

**NOTE:** The PRO-CTCAE should be completed each time a Symptom/Toxicity Assessments is completed.

The total length of this assessment is dependent on the assessment time point. One of the lengthiest assessments will occur at Baseline (FACT-G, PROMIS-fatigue, FAACT-subscale, FACIT-diarrhea subscale, FBSI, PRO-CTCAE) is 80 multiple choice items. The anticipated time to complete all items is roughly 15-20 minutes. Assessments prior to cycles 4, 7 and 13 will also include the ECOG-ACRIN Medication Adherence Scale Modified from the Morisky Index that will include 8 multiple choice or yes/no items and will take roughly 2-3 minutes. This assessment schedule corresponds to the first, second, and fourth disease assessments. We have scheduled PRO assessments with standard clinic office visits to minimize participant and site burden, thus minimizing the risk of missing PRO data. Assessments to be administered at every cycle (FBSI, PRO-CTCAE) will include 21 multiple choice items and will take 4-5 minutes to complete.

PRO assessments at treatment discontinuation and 4 weeks post-treatment discontinuation for all participants regardless of the reason for treatment discontinuation (toxicity, progression) will provide valuable information on HRQL and symptom burden. As noted by Rini et al. HRQL can appear to improve overall as the trial progresses due to participant selection bias. Participants with poorer performance status, more aggressive disease, and greater treatment toxicities come off treatment earlier. We may observe a high rate of attrition due to progression of illness. Patients on EE are expected to remain on treatment longer than patients on EP due to anticipated benefit in PFS. To obtain an unbiased assessment of HRQL and treatment toxicities, PRO assessment at the end of treatment and a short period of time following end of treatment (4 weeks) for all participants is needed. Otherwise, PRO assessments only capture data on participants who remain on treatment and are likely to be healthier, therefore, presenting a biased source of data that will likely indicate that HRQL improves over time. In addition, the assessment 4 weeks post-end of treatment will evaluate whether entinostat-related symptoms resolve within 4 weeks. This design (retaining participants who discontinue treatment) has been employed with other PROs studies such as the side effect sub-study of MA.27.

Rev. Add7

A PRO measure of breast cancer-specific symptoms will be administered at baseline, and every 28-day cycle for the first six months after randomization, and then every two cycles between 6 months and 1 year. After 1 year, the FBSI will be administered on the same schedule as tumor assessments until disease progression. The FBSI will be administered more frequently to allow for an assessment of time to treatment deterioration (TTD), a critical secondary endpoint.

The PRO measure of adherence to therapy, the Medication Adherence Scale - , will be administered as outlined in Section [5.6.3](#) (before Cycle 4, 7, 13, and end of protocol therapy). With the exception of baseline, these assessment time points correspond with other study PRO.

The FBSI and Medication Adherence Scale include 8 and 8 items each and the anticipated time to complete the 16 items is roughly 5-6 minutes. Please note there will be one Medication Adherence Scale form completed for each agent (entinostat/placebo and exemestane).

Rev. Add7

